Study Title: Louisiana Community-Engagement Alliance (LA-CEAL)

1. Study aim, background, and design

In August 2020, Louisiana (LA) ranked first in the US for COVID-19 cases by population with a case rate of 2,960 per 100,000 and fifth in deaths by population with a death rate of 97 per 100,000.¹ Furthermore, there were disturbing demographic trends in LA with Blacks representing the highest percentage of cases (40.2%) and second highest percentage of deaths (48.7%).² At that time, vaccines for prevention of COVID-19 were in development.³ To reduce COVID-19-related morbidity and mortality, an approved vaccine needed to be disseminated with rapid uptake in the community. Mistrust of the health care system and experimentation create barriers to rapid and widespread acceptance of novel COVID-19 preventive and therapeutic interventions (including vaccines) among underrepresented groups.⁴ The objective of this study is to **rapidly implement and evaluate the HALT-COVID program designed to address barriers and increase knowledge about COVID-19, vaccines, and availability of trials that informs decision-making about willingness to participate (WTP) in COVID-19 prevention (e.g., vaccines) and therapeutic initiatives and trials in underrepresented Louisianians.**

To accomplish this objective, we will conduct a **randomized controlled trial** to test the effectiveness of HALT COVID educational outreach by HALT COVID Ambassadors. HALT COVID Ambassadors will receive training to answer common vaccine questions & address misconceptions; conduct motivational interviewing (which has shown promise for reducing vaccine hesitancy); implement basic behavioral economics and related strategies to remove barriers to vaccination; and assist with scheduling vaccine appointments. Participants will be identified via multiple recruitment strategies including:

- **Random sample drawn from FQHC EHR data downloads:** EHR data downloads of adult patients seen in the last year will be used to draw random samples of persons to be contacted by telephone.
- **In-clinic recruitment:** via LA-CEAL staff who will directly approach clinic patients to inform on study activities, gain consent and assess eligibility.
- **Snowball sampling techniques:** potential (i.e., persons who have been screened, regardless of final eligibility determination) and enrolled participants will have the opportunity to refer persons they feel may be interested in participating.

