- **Referrals from partners (including FQHC, FBO, and pharmacy partners):** persons will be recruited via flyers that are posted at partner locations or distributed at community events, in addition to in-person recruitment and telephone-based recruitment by partner staff using member/patient lists or other referrals.
- **Ambassador identification and enrollment:** HALT-COVID Ambassadors will have opportunities to recruit persons using contacts made during fieldwork and community events.
- **Internet (digital displays & video) and radio advertisements** developed and disseminated by communications and public relations partner.

Eligibility will be based on the following criteria: vaccine hesitancy, age ≥ 18 , Black, able to understand and speak English, and willing to engage with the HALT COVID Ambassador via in-person or virtual sessions exploring their own questions and concerns about vaccines. A total of 100 individuals will be enrolled into the trial and randomized to intervention (engagement by the Ambassador over a 1-month period) or usual care (no extra engagement). Baseline, 1-month, and 2-month follow-up surveys will assess for change in vaccine hesitancy.

2. Subject Population

Using the following criteria, we will enroll up to 100 participants from patient populations of partner FQHCs:

Inclusion criteria: Vaccine hesitancy; age ≥ 18 years; Black; ability to understand and speak English; willingness to engage with the HALT COVID Ambassador via in-person or virtual sessions exploring their own questions and concerns about vaccines

Exclusion criteria: Unable or unwilling to give informed consent

Multiple strategies will be used to recruit participants including telephone calls to a random sample of adult patients served in the past year (identified in the EHR); in-clinic recruitment by LA-CEAL staff of clinic patients from partner FQHCs; snowball sampling methods, offering potential and enrolled participants the opportunity to refer others; referrals from FQHC, FBO pharmacy, and other partners using flyers, direct communication at partner locations and community events, and telephone-based recruitment to identify and recruit potential participants; Ambassador identification and enrollment during fieldwork and community events; and internet (digital displays and video) and radio advertisements.

Eligibility criteria will be confirmed prior to enrollment into the study.

3. Procedure

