After obtaining verbal consent, study staff will verify participant contact information, collect alternate contact information for a friend or family member who is likely to be able to reach the participant in the event the study staff cannot, conduct a baseline questionnaire, and reveal the results of the randomization procedure conducted by the LA-CEAL Study and Data Coordinating Center staff. Participants will be randomly assigned to intervention (HALT COVID Ambassador engagement) or usual care. Participants randomized to the intervention will be engaged over a one-month period in discussions by the HALT COVID Ambassador; identified concerns or barriers around vaccination will be addressed, drawing upon the training and resources provided through the LA-CEAL program. We anticipate a total of 3-4 engagements over the month, each lasting 30 minutes to 1 hour. Discussions will take place in-person at a location mutually agreed upon by the participant and Ambassador, or virtually via telephone or web-based video platform (e.g., Zoom). Usual Care participants will not receive any additional outreach during this one-month period. After one month, all participants will be re-contacted via telephone by LA-CEAL staff to complete a month 1 follow-up survey. Following a one-month maintenance period (no intervention delivery), all participants will be re-contacted via telephone by LA-CEAL staff to complete a month 2, follow-up sustainability survey. Study staff will contact participants by text or phone to confirm and remind of all study and Ambassador visits.

4. Risks

The risk of physical, psychological, social, or legal harm associated with participation in all components of this study is minimal:

- Though not sensitive in nature and widely used in social science research, participants may feel uncomfortable responding to some of the survey questions; participants will be informed that they do not have to answer any question they do not want to answer and that they can stop participating at any time without penalty.
- Participants may find it inconvenient to take time to participate in the study. All study activities will be arranged at a time that is convenient for participants. The option to complete study activities via telephone or Zoom will also ease the burden of participation for participants.

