- There is a small risk of unauthorized disclosure of participants' responses, which will be prevented by following a strict protocol for data handling and rigorous training of study staff:
 - All electronic study records will be stored with password protection. All paper study records will be locked in a secure study office. Data will be accessible only by study staff with approval from the PI.
 - The data will be retained without identifiers in a secure location for possible use in a future project, which will be consistent with the original research purpose.
 - Data may be shared with the NIH or other researchers upon request. Any data shared with the NIH or other researchers will not contain identifying information.
 - Identifiers will be stored in REDCap for the purposes of study management and follow-up. Study data will be stored separate from identifiers and a master key linking study data to identifiers will

be stored electronically in a separate REDCap database. Upon completion of all data collection and verification activities, records linking identifying information to study data will be destroyed.

5. Benefits

Individuals randomized to the intervention could benefit from engagement with the HALT COVID Ambassador which provides COVID-19 information and messages that may change their attitudes toward vaccines and remove barriers, thereby leading to vaccination and reduction in risk of severe COVID-19 infection. The knowledge to be gained may benefit society in general by providing evidence about the effectiveness of an approach for reducing vaccine hesitancy and increasing vaccine uptake.

6. Remuneration

Participants who complete the baseline and follow-up surveys will receive remuneration in the form of a \$25 gift card for each survey completed (up to \$75).

In addition, potential and enrolled participants will receive a \$10 gift card for reimbursement of time used to recruit others (per person ultimately enrolled, up to five persons per referring individual).

Participants who are randomly assigned to the intervention will also receive remuneration in the form of a \$15 gift card for each Ambassador session completed (up to \$60).

7. Costs

There will be no costs to the participant for participating in this research study.

8. Consent process and documentation

Participants will be identified via multiple recruitment strategies:

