- **Ambassador identification and enrollment:** HALT-COVID Ambassadors will have opportunities to refer persons using contacts made during fieldwork and community events. The IRB-approved recruitment script will be provided to Ambassadors for use in recruitment efforts. In addition, study flyers and contact information for study staff will be provided to Ambassadors for passing on to potential participants. Interested individuals will contact LA-CEAL study staff through the study telephone number or will give their contact information (name and phone number) to the Ambassador for contact by LA-CEAL study staff. A recruitment script will be used to introduce the study and a consent script that explains the study purpose, procedures, risks and protections, and benefits will be read to interested patients. Verbal consent will be obtained and eligibility will be assessed before administration of the baseline survey. We are requesting a *waiver of HIPAA Authorization* and a *waiver of documentation of informed consent* for this study activity given the nature of the risk associated with participating in the study (minimal) and the fact that most or all study activities will be conducted via telephone or web-based video platform (e.g., Zoom).
- **Internet (digital displays & video) and radio advertisements:** A communications and public relations firm will develop and disseminate internet (using both video and digital displays) and radio advertisements. Prospective participants will be directed to self-complete a virtual pre-screening/interest form. Those meeting initial inclusion criteria and providing contact information will be contacted by the LA-CEAL research team. A recruitment script will be used to introduce the study and a consent script that explains the study purpose, procedures, risks and protections, and benefits will be read to interested patients. Verbal consent will be obtained and eligibility will be assessed before administration of the baseline survey. We are requesting a *waiver of documentation of informed consent* for this study activity given the nature of the risk associated with participating in the study (minimal) and the fact that most or all study activities will be conducted via telephone or web-based video platform (e.g., Zoom).

9. References

1. Centers for Disease Control and Prevention. CDC COVID Data Tracker. <https://www.cdc.gov/covid-data-tracker/#cases>. Published 2020. Updated Aug 19 2020. Accessed Aug 19 2020.

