2. Louisiana Department of Health. COVID-19. <https://ldh.la.gov/Coronavirus/>. Published 2020. Updated Aug 19 2020. Accessed Aug 19 2020.
3. World Health Organization. DRAFT landscape of COVID-19 candidate vaccines. World Web site. <https://www.who.int/publications/m/item/draft-landscape-of-covid-19-candidate-vaccines>. Published 2020. Accessed Aug 24 2020.

Statistical Analysis Plan

Baseline demographics will be summarized using means and standard deviations or proportions as appropriate. Between-group differences in the proportions of participants for each outcome will be tested using Pearson's chi-squared tests.

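### Does the SAP's chi-squared test need an allowance for participants who share an Ambassador?

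*Combined protocol and SAP*

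**What the plan says.** The Statistical Analysis Plan is two sentences long. The first covers baseline summaries. The second is the only inferential statement: "Between-group differences in the proportions of participants for each outcome will be tested using" Pearson's chi-squared tests. It gives no confidence interval, model or allowance for clustering.

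Section 1 gives the purpose as a randomized trial "to test the effectiveness of HALT COVID educational outreach by HALT COVID Ambassadors". One hundred individuals are "randomized to intervention (engagement by the Ambassador over a 1-month period) or usual care (no extra engagement"). Section 3 adds that "Participants randomized to the intervention will be engaged over a one-month period in discussions by the HALT COVID Ambassador", with 3-4 sessions of 30 minutes to 1 hour expected. Usual care gets no additional outreach in that month.

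Ambassadors also help to find participants. Section 1 says "HALT-COVID Ambassadors will have opportunities to recruit persons using contacts made during fieldwork and community events", and section 8 says "HALT-COVID Ambassadors will have opportunities to refer persons using contacts made during fieldwork and community events". Under section 8, LA-CEAL study staff then handle the contact. Neither section says that Ambassadors go on to serve the people they referred.

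Section 5 hopes to benefit society by "providing evidence about the effectiveness of an approach for reducing vaccine hesitancy and increasing vaccine uptake". The number of Ambassadors, their caseloads and the rule for assigning participants to them are not stated.

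**The concern.** This is a partially nested design: people are randomized one by one, but one arm is then treated by a limited set of providers. The intervention is personal (motivational interviewing, answering questions, help with appointments), so some Ambassadors may well persuade better than others. If they do, and each sees several participants, outcomes in that arm are correlated within Ambassador. The intervention proportion then varies more than a binomial proportion would, and chi-squared uses too small a standard error.

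At stake would be a claim that Ambassador outreach works as a general approach, with a p-value that reflects variation between participants but not between Ambassadors. The sentence in section 5 can be read as aiming at that wider claim. With few Ambassadors, one very good one could carry the result.

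**Working it through.** **Inputs.** From the documents: 100 individuals, individually randomized (sections 1 and 2); Ambassador contact in one arm only (section 3); chi-squared as the only test (SAP). Assumed, because not stated: 50 per arm, two-sided 5%, equal caseloads, no dropout, K Ambassadors and an ICC of 0.02 to 0.10. The plan has no figure of its own to reproduce.

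**Type I error for a zero average effect.** With m = 50/K participants per Ambassador, the design effect in the intervention arm is DE = 1 + (m - 1) × ICC. At equal proportions, the variance of the difference is multiplied by V = (1 + DE)/2. The nominal 5% test then rejects with probability 2 × (1 - Φ(1.96/√V)).

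| K | m | V at ICC 0.02 / 0.05 / 0.10 | Error at ICC 0.02 / 0.05 / 0.10 |
|---|---|---|---|
| 25 | 2 | 1.010 / 1.025 / 1.050 | 5.1% / 5.3% / 5.6% |
| 10 | 5 | 1.040 / 1.100 / 1.200 | 5.5% / 6.2% / 7.4% |
| 5 | 10 | 1.090 / 1.225 / 1.450 | 6.0% / 7.7% / 10.4% |
| 3 | 16.7 | 1.157 / 1.392 / 1.783 | 6.8% / 9.7% / 14.2% |

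Example, K = 5 and ICC 0.05: DE = 1 + 9 × 0.05 = 1.45; V = 2.45/2 = 1.225; 1.96/√1.225 = 1.771; error 7.7%. With ICC 0, or one participant per Ambassador, V = 1 and the error is 5.0%. Beta-binomial simulation with a 30% rate in both arms agrees (7.7% for K = 5, ICC 0.05).

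**What that null means.** A zero average effect with a positive ICC requires some Ambassadors to raise the outcome rate and others to lower it. At a 30% rate, the between-Ambassador standard deviation is √(ICC × 0.30 × 0.70): √0.0105 = 10.2 points at ICC 0.05 and √0.021 = 14.5 points at ICC 0.10. About half the Ambassadors would be doing worse than usual care. If no Ambassador has any effect, chi-squared keeps its 5% level.

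**Coverage.** The SAP plans no confidence interval, so this describes an interval that analysts might add. At assumed rates of 45% and 20%, the simple 95% interval has half-width 1.96 × √(0.45 × 0.55/50 + 0.20 × 0.80/50) = 17.7 points. Its coverage, enumerated exactly with a beta-binomial intervention arm, is 94.4% at ICC 0. The fair baseline is therefore 94.4%, not 95%. At ICC 0.05:

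- K = 25: 94.0%, a loss of 0.4 points
- K = 10: 92.9%, a loss of 1.5 points
- K = 5: 91.0%, a loss of 3.4 points

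**What a partially nested sensitivity analysis would add.** The version considered regresses the binary outcome on arm. Ambassador is the cluster in the intervention arm and each usual-care participant is a cluster of one, with CR2 standard errors and Satterthwaite degrees of freedom. Simulated results:

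- Power at 45% vs 20% and ICC 0.05, against chi-squared: 76% vs 77% (K = 25), 69-71% vs 76% (K = 10), 57-62% vs 75% (K = 5).
- Mean half-width in the same setting: 18.3 points (K = 25), 19.3-19.8 (K = 10), 21.2-22.8 (K = 5).
- K = 3, ICC 0.10, zero average effect: it still rejects 7.1-7.8%.
- If the correlation comes only from who referred whom, with no intervention effect, it rejects 3.2-4.6% (K = 10) or 2.6-4.5% (K = 5), while chi-squared stays near 5%.

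**The case for a change.** The strongest case for a change is that it would be cheap and could not be made later. Ambassadors are the intervention, readers will take a positive result as being about the approach, and if nobody records who served whom the question may become unanswerable. With 3 to 5 Ambassadors and an ICC of 0.05 to 0.10, the error for the wider claim is 7.7% to 14.2%, which is not trivial. Chi-squared would stay the main test, so its power is untouched.

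Part of this stands. The arithmetic is right, the direction is always towards too little uncertainty when the conditions hold, and a report should say how many Ambassadors delivered the sessions.

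It does not make the planned test wrong. Whether providers are treated as fixed or as a sample is a choice on which reasonable statisticians differ. Section 1 names one program's Ambassadors, and nothing describes them as drawn from a wider group. The Benefits sentence is a general hope, not a defined target of estimation. The larger error rates also need few Ambassadors and a high ICC, neither of which is documented, together with a null in which about half the Ambassadors do harm.

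The added analysis is weakest where it would matter most. With many Ambassadors it hardly differs from chi-squared. With very few it loses much power or still over-rejects, and the sensible response is to limit the wording of the conclusion, which needs no new model.

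**Conclusion.** No change to the plan. Chi-squared suits individual randomization. It is valid for the null of no effect on anyone and acceptable for the Ambassadors who took part. Understated uncertainty arises only for a generalization beyond them, and only if Ambassadors are shared and differ in effect.

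Under the assumptions above (50 per arm, equal caseloads, no dropout, Ambassador effects that differ in direction but average zero), the error is at most about 6.2% with 10 or more Ambassadors and ICC up to 0.05. It is 6.0% to 10.4% with 5 Ambassadors at ICC 0.02 to 0.10. It is 5.0% if no Ambassador is shared or the ICC is 0. The true size cannot be set from the documents and may be negligible.

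What is missing is description: how many Ambassadors there were, how participants were assigned to them, and how far the conclusion is meant to reach. Competent analysts would supply this in the report and would word the conclusion narrowly if Ambassadors were very few. A prespecified nested analysis with no stated consequence for the conclusion would add little.
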